14.6 DATA SECURITY AND STORAGE

Databases at the central site will be stored on an encrypted server in a temperature-controlled locked room at the Proctor site, and off-site backups will be maintained. Backup encryption keys will be maintained off-site in a secure vault. Database procedures will include full transaction logs. The DSMC can make requests to have access to the data at any point during the course of the study.

14.7 ESTIMATION OF DISEASE PREVALENCE

Computerized randomization is utilized to prepare samples for pooling. PCR pooling will be conducted stratified by study community. All samples will be pooled in pools of 5. We will automatically unpool any positive pools results tabulated by development team.

14.8 SAMPLE ORGANIZATION AND STORAGE

Samples are organized according to collection time point. A detailed sample storage chart is created by the Database Manager for each visit and all samples are linked with the study database.

Samples will be stored at the Ralph and Sophie Heintz Laboratory at the Proctor Foundation in San Francisco in -80° freezers. A protocol to monitor the temperature of the freezer will be established.

15. STATISTICAL METHODS

Statistical analyses and sample size calculations are detailed in a separate Statistical Analysis Plan.

16. MOP CHANGE LOG

Date	Version	Edit

## 2. Introduction

### 2.1. Background and rationale

*[From the NIH grant application]*

In this study, we will conduct a randomized evaluation of stopping versus continuing mass azithromycin distribution. Although WHO guidelines indicate that evaluation units with TF prevalence above 10% be treated for 3-5 years, this is an arbitrary threshold and trachoma may disappear in regions with declining prevalence in the absence of antibiotic intervention.

Measurement of TF is noisy, as it relies on field grades. Despite standardization, training, and certification, substantial variation between graders likely exists. Districts with measured prevalence in a given window above and below the threshold may only by chance be above or below the threshold and thus receiving treatment. If communities slightly above the 10% threshold are in reality similar to those below in true prevalence of infection, antibiotic treatment for these communities would not be expected to provide additional benefit. If trachoma is disappearing due to secular trends in improvements in sanitation and hygiene in these communities, stopping azithromycin distribution above the threshold may be possible. Early cessation of antibiotics in regions with borderline prevalence would reduce antibiotic selection pressure, which may prevent emergence of resistance in potentially pathogenic organisms.

### 2.2. Objectives

**Specific Aim 1.** Determine if local elimination of ocular *Chlamydia trachomatis* can be achieved in the absence of azithromycin intervention.

*We hypothesize that stopping mass azithromycin in communities with up to 20% prevalence of TF will be non-inferior to continuation of annual mass azithromycin at 36 months.*

**Specific Aim 2.** Assess ongoing true transmission of infection in low TF areas by evaluating alternative indicators.

*We hypothesize that alternative indicators can supplement or even replace TF, and that the 95% confidence interval of the estimate for true infection from a hidden Markov model including alternative indicators of transmission will include zero (elimination).*

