2.3.3 SAMPLE SIZE

40 communities per arm (80 total) will be included in the study. Please see Statistical Analysis Plan (SAP) for same size calculation details.

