8.7 CONJUNCTIVAL SWAB COLLECTION

A random sample of 50 children <10 years old will undergo conjunctival swabbing at 0 and 36 months. Swabs will be processed for *C. trachomatis*. Samples will be processed within in pools of 5. Any positive pools will be unpooled and processed individually. Swabs will be labeled with a unique barcode in the field, which will link to a unique identification number. The number will be linked with the individual's census entry during swab collections in the field.

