### **6.2.1. Aim 2 Analysis: Hidden Markov Model for Infection Prevalence**

The primary analysis for Specific Aim 2 will be a hidden Markov model, conducted at the community level using a truncated normal distribution. Analyses will be conducted in the continuation and stopping arms separately, as distribution of azithromycin likely affects the relationship between the indicators. This will allow for understanding of the best tools for surveillance both with and without azithromycin treatment. This model will use four diagnostic tests – TF, TI, ocular chlamydia, and seropositivity to CT694 and Pgp3 separately, and will not assume that any of the tests are a gold standard. The truncated normal distribution allows several options to handle the expected high density of communities with zero prevalence, including zero-inflation or a free fitted parameter. The model will incorporate delays in TF and serology, as TF follicles can take months or longer to recede and serologic measurements are long-lasting. The hidden Markov model will be fit to the prevalence of the indicators for trachoma transmission to estimate the prevalence of the true hidden prevalence of trachoma. For the test of treatment, we will assess the effect of continuation versus stopping on alternative indicators alone and in combination. Absence of an effect of treatment will suggest that there is no true infection in the community. In practice, we have found some degree of model exploration necessary, and our publications will include all explored models. Estimation will be conducted using the standard Metropolis algorithm (as we have conducted before).

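### The plan's only operational meaning of elimination is an interval that includes zero or an absent treatment effect, and neither supports it

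*SAP*

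**What the plan says.** SAP 2.2 states the Aim 2 hypothesis that "the 95% confidence interval of the estimate for true infection from a hidden Markov model including alternative indicators of transmission will include zero (elimination"), so the bracketed word equates an interval reaching zero with elimination.

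SAP 6.2.1 (Aim 2 Analysis) adds a second reading, for the contrast between arms on the alternative indicators: "Absence of an effect of treatment will suggest that there is no true infection in the community". The same section says the model is "conducted at the community level using a truncated normal distribution", that "Analyses will be conducted in the continuation and stopping arms separately", and that "The truncated normal distribution allows several options to handle the expected high density of communities with zero prevalence, including zero-inflation or a free fitted parameter". Estimation is by the Metropolis algorithm. Some model exploration is expected, and all explored models are to be published.

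Aim 1 in SAP 2.2 asks whether local elimination "can be achieved in the absence of azithromycin intervention". The hypothesis under it is noninferiority at 36 months.

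No section sets an upper limit on prevalence, a maximum interval width or an equivalence margin for Aim 2. The 3% margin in SAP 3.3.1, 3.4 and 6.2.1 (Aim 1) applies to the difference between arms.

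**The concern.** An interval that includes zero shows that infection was not distinguished from zero. It does not show that infection is absent or very low. Fewer communities, noisier indicators or a looser model widen the interval and make zero easier to reach. Aim 1 works the other way: there the upper limit must fall below a margin, so imprecision counts against the claim.

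The null-effect reading has a further problem. Two arms with the same persistent infection show no effect. Protocol 10.4 itself notes that frequent mass distribution has failed to bring elimination where trachoma is highly prevalent (a different setting from this one, but it shows that treatment and persistence can coexist). A null contrast could also reflect weak delivery: under SAP 4.2 the national programme carries out the month 12 and 24 distributions, and the study plans no visits in between.

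At stake is whether the trial could describe a stop-arm result as elimination when the data only fail to exclude zero.

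**Working it through.** **Inputs.** 40 communities per arm: "40 communities per arm (80 total) will be included in the study" (Protocol 2.3.3). 50 children each: "A random sample of 50 children <10 years old will undergo conjunctival swabbing at 0 and 36 months" (Protocol 8.7). One arm therefore has 40 × 50 = 2,000 children. SD of community prevalence 0.05, baseline correlation 0.5 and residual SD about 0.043 come from SAP 3.3.1. Two-sided 95% intervals come from SAP 4.1. The SDs of 0.02, 0.03 and 0.08 below are my assumptions, to show a range.

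**The plan's own figures.**
- Residual SD: 0.05 × √(1 − 0.5²) = 0.0433, as stated.
- SAP 3.3.2 gives the only precision figures for Aim 2, and they concern sensitivity and specificity, not prevalence. With p = 0.95, 1.96 × √(0.95 × 0.05 / 100) = 4.27%, close to the stated 4.2%. With n = 1,900 the same formula gives 0.98%, not the stated 0.1%. That is a separate error and nothing below uses it.

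**Interval reading.** The documents give no standard error for the hidden Markov estimate, so I use a simple community mean of PCR prevalence as a stand-in. The half-width is 1.96 × SD / √40:

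| SD | Half-width (points) | × 2,000 children | Most positives that still include zero |
|---|---|---|---|
| 0.05 | 1.55 | 30.99 | 30 |
| 0.03 | 0.93 | 18.6 | 18 |
| 0.02 | 0.62 | 12.4 | 12 |

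The chance that the interval includes zero at true prevalence μ is Φ(1.96 − μ√n/SD). With SD 0.05 and μ = 2%, it is 28% with 40 communities, 57% with 20 and 76% with 10. A beta-binomial simulation with t intervals gives 12%, 65% and 95%. The levels differ but the direction is the same: less data makes the criterion easier to meet. At μ = 1% with 40 communities, the formula gives 12%, 76% and 88% for SD 0.02, 0.05 and 0.08.

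**Dependence on interval type.** Suppose the prevalence parameter is bounded at zero with a continuous posterior. An equal-tailed 95% interval then leaves 2.5% of the probability below its lower limit, so that limit is always above zero. For an unconstrained estimate of 0 with standard error 0.05/√40 = 0.79 points, truncation at zero gives 0.02% to 1.77%. A highest-density interval can touch zero when the posterior mode is there, and a model with a point mass at zero may include it. The same data can therefore meet or fail the criterion.

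**Null-effect reading.** The standard error of the arm difference is 0.0433 × √(2/40) = 0.97 points.
- The chance of no significant effect is 95% at a true difference of 0, 82% at 1 point, 46% at 2 points and 13% at 3 points.
- The 2-point value is Φ(1.96 − 2/0.968) = Φ(−0.106) = 0.46.
- SAP 3.3.1 gives TF the same SD and correlation, so these figures apply to it too.
- Simulating equal prevalence of 3%, 5%, 10% and 20% in both arms gives no significant effect in 95% to 96% of trials, with infection present in every one.

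**The case against.** The strongest reply is that neither sentence is a decision rule. One is introduced as a hypothesis and the other says only that a null result will suggest absence. All explored models will be published, and the hidden Markov estimate is not among the primary or secondary outcomes in SAP 6.1. This stands as a limit on the wording: the plan does not say that elimination will be declared. It does not remove the problem, because no other operational meaning of elimination is given.

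A reader might infer that the case for stopping treatment rests on these readings. The documents do not support that. The stop-versus-continue comparison is Aim 1, with a two-sided 95% interval against a fixed margin, and imprecision counts against it. Nor does any analysis section say that noninferiority establishes elimination; the word appears only in the aim's opening sentence.

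A reader might also infer that imprecision always helps an elimination claim. That holds only where the interval can reach zero. With an equal-tailed interval and a continuous posterior bounded at zero, the criterion could never be met. The SAP does not say which case applies.

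Finally, the counts come from a symmetric interval on PCR alone, with an SD assumed for prevalence after one year of treatment and held fixed as prevalence falls. They are illustrations, as the gap between formula and simulation shows.

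**Conclusion.** The point holds for Aim 2. As worded, the two readings do not support elimination: where zero can be reached, the first becomes easier to meet as precision falls, and the second is expected about 95% of the time when infection persists equally in both arms. The first is also undefined until interval type and zero handling are fixed.

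The 95% follows from the two-sided 5% level. The 46% chance of missing a 2-point difference rests on the SAP's residual SD and 40 communities per arm. The range of 12 to 30 positives among 2,000 rests on the stand-in estimator and SDs of 0.02 to 0.05. The direction does not depend on those values.

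For Aim 1 this is only a caution about reporting: a between-arm difference says nothing about the level of infection, so noninferiority alone should not be described as local elimination.

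**What to change.** 1. In SAP 6.2.1 (Aim 2 Analysis), delete the sentence on absence of an effect, or reword it to say that a null contrast does not show absence of infection.
2. In SAP 2.2, replace the includes-zero wording with: elimination is supported for an arm only if the upper 95% limit of its estimated true prevalence at 36 months is below a near-zero threshold, justified by the sponsor and fixed before unmasking.
3. Name in advance the interval type and zero handling that decide this. Other explored models can still be reported.
4. Report Aim 1 as noninferiority only, with no local-elimination claim unless the stop arm also meets item 2.

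The 3% noninferiority margin should not serve as the threshold, because it is a difference between arms. On the stand-in interval at SD 0.02, an upper limit below 3% would allow a mean up to 3 − 0.62 = 2.38%, or 47 positives of 2,000. The lower limit would then be 2.35 − 0.62 = 1.73%, so infection would be clearly present. The criticised reading allows 12 at that SD.

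For scale, no positives among 2,000 gives an upper limit of 1 − 0.025^(1/2000) = 0.18%, ignoring clustering and test error.

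The cost is SAP wording and no new data. The downside is that a threshold must be justified and an elimination claim then needs precise evidence.

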## 3. Study Methods

### 3.1. Trial design

ARRET is a parallel, community randomized controlled trial to evaluate if mass azithromycin distribution can be discontinued in low prevalence districts. We will randomize *grappes* (approximately the size of a small village) in Niger in equal allocation (1:1) to continuation of annual mass azithromycin distribution to the entire community or stopping azithromycin treatment. For the remainder of this SAP, we will refer to *grappes* as communities. The trial will not include a placebo and will be single-masked (investigators masked). All communities will undergo identical census and monitoring. The continuation arm will receive active azithromycin

and the stopping arm will stop treatment. The trial will measure outcomes at a single timepoint, 36 months after baseline.

### 3.2. Randomization

Study communities will be randomized into one of the two study arms after the baseline monitoring visit. Randomization will occur after the baseline monitoring visit to reduce the potential for differential outcome assessment at the baseline visit. The randomization sequence will be generated by the trial biostatistician in San Francisco using a random number generator, without stratification or blocking. The randomization sequence will be masked from study investigators until the primary analysis is completed by the trial's biostatistician.

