2.3.2 STUDY AREA

This study will be conducted in two districts in Maradi Region, Niger. The districts of Guidan Roumdji and Mayahi have approximately 1 million inhabitants. Per the most recent trachoma impact surveys, conducted in July 2018, these districts have TF prevalence up to 20%. Annual mass azithromycin distribution started in 2008 in Guidan Roumdji and Mayahi.

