4.2.3 TREATMENT ARM RANDOMIZATION

Study communities will be randomized into one of the 2 study arms after the baseline monitoring visit. Randomization will occur after the baseline monitoring visit to reduce the potential for differential outcome assessment at the baseline visit. The randomization sequence will be generated by the trial biostatistician in San Francisco using a random number generator, without stratification or blocking.

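### The allocation method as worded does not guarantee 40 communities per arm and leaves balance between the two districts to chance; restricting it and adding district to the model would cost almost nothing

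*SAP*

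**What the plan says.** Protocol 4.2.3 and SAP 3.2 use the same words: the trial biostatistician generates the sequence "using a random number generator, without stratification or blocking". On arm sizes, Protocol 2.3.3 says "40 communities per arm (80 total) will be included in the study", SAP 3.3.1 repeats 40 per arm, and SAP 3.1 describes randomisation "in equal allocation (1:1) to continuation of annual mass azithromycin distribution to the entire community or stopping azithromycin treatment". Neither document says whether the arm totals are fixed in advance or each community is drawn independently.

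On geography, Protocol 2.3.2 says "This study will be conducted in two districts in Maradi Region, Niger". It does not say how many communities come from each. On timing, "Study communities will be randomized into one of the two study arms after the baseline monitoring visit" (SAP 3.2), and Protocol 5 places the census of the selected communities before randomisation. District is recorded on the Field Form (Protocol 14.5.3).

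The primary model in SAP 6.2.1 (Aim 1) regresses community-level prevalence at 36 months on arm and baseline prevalence; district is not a covariate. SAP 6.3 refers to a permutation test in which communities with missing outcomes still receive allocations.

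**The concern.** A stated total of 40 per arm needs a method that fixes the totals, and the text does not describe one. District is the most obvious grouping of the communities, and it is handled neither at allocation nor in the primary model. Trials often avoid restriction because staff might predict the next assignment. That reason is absent here, since every community is selected, censused and examined before allocation.

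Three things are at stake. The first is whether the planned arm sizes will occur. The second is whether one district could be over-represented in one arm, in a comparison judged against a 3-point margin. The third is whether the permutation test has a defined reference distribution: it must re-draw allocations by the scheme actually used, and the plan does not say which scheme that is.

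**Working it through.** **Inputs.** From SAP 3.3.1: SD of community prevalence 0.05, baseline to follow-up correlation 0.5, margin 3%, 40 per arm, two-sided α 0.05. The number of communities per district is not given, so I take a range from 40/40 to 20/60. The size of any district difference is also not given and is treated as an assumption.

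**1. The plan's own power figure.** Residual SD = 0.05 × √(1 − 0.5²) = 0.0433. With a true difference of zero,

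power = Φ(0.03 / (0.0433 × √(1/n₁ + 1/n₂)) − 1.96).

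At 40/40: 0.03 / (0.0433 × 0.2236) = 3.10, and Φ(3.10 − 1.96) gives 87.3%. This agrees with the stated figure of at least 80%.

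**2. Arm sizes if the 80 draws are independent.** The size of one arm is Binomial(80, 0.5).

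- P(exactly 40/40) = C(80,40)/2⁸⁰ = 8.9%
- P(35/45 or worse) = 31.4%
- P(30/50 or worse) = 3.3%
- 95% range for one arm: 31 to 49

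**3. What unequal arms cost.** The same power formula gives 86.7% at 35/45, 85.5% at 31/49 and 85.1% at 30/50. Averaged over the binomial distribution it is 86.8%. Power drops below 80% only if the smaller arm has fewer than 23 communities, which has probability about 0.00007.

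**4. District balance.** Let A be the number of communities in one district. If arm totals are fixed at 40/40 without strata, the number x from that district in one arm is hypergeometric, and the difference in district share between arms is 2|x − A/2|/40. For independent draws the same difference follows from two separate binomials.

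| Communities per district (assumed) | Independent: ≥10 points | Independent: ≥20 points | Fixed 40/40: ≥10 points | Fixed 40/40: ≥20 points |
|---|---|---|---|---|
| 40/40 | 43.4% | 9.3% | 50.3% | 11.7% |
| 30/50 | 37.4% | 7.0% | 48.9% | 10.5% |
| 20/60 | 33.5% | 4.5% | 43.9% | 6.9% |

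The SD of the difference is about 10 to 11 points throughout. Fixing the arm totals alone does not improve district balance; stratification brings the difference to about zero.

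**5. What district imbalance could do.** The SE of the arm difference is 4.33 × √(2/40) = 0.97 points. With a 20-point imbalance, an assumed 2-point district gap at month 36 after baseline adjustment shifts the estimate by 0.20 × 2 = 0.4 points. An assumed 5-point gap shifts it by 0.20 × 5 = 1.0 point.

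**6. Precision from stratifying and adjusting (equal districts assumed).** The 95% CI half-width is 1.99 × SD × √(2/40). Removing a gap g between two equal districts reduces the variance by g²/4.

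- No gap: 1.99 × 4.33 × 0.2236 = 1.93 points
- g = 2: SD = √(18.75 − 1) = 4.21, half-width 1.87
- g = 5: SD = √(18.75 − 6.25) = 3.54, half-width 1.57

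**The case against.** A reader might infer that the plan contradicts itself and fails to deliver 1:1 allocation. The text does not support that. Independent draws with probability one half are 1:1 in expectation. The wording also fits ranking the 80 communities by random number and taking 40, which gives exactly 40/40. The 8.9% applies only to independent draws. The gap is an unspecified mechanism, and step 3 shows that its cost in power is trivial.

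A reader might also infer that the districts will be unbalanced and the result therefore biased. Imbalance is a chance event. It causes no bias on average, its variance is already part of the residual SD, and the planned confidence interval stays valid. The shifts in step 5 are about one SE or less, and the baseline-prevalence covariate should absorb part of any district difference.

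Finally, a reader might infer that the districts are known to differ. The documents show no such thing. Protocol 2.3.2 gives both districts the same TF ceiling, the same survey date and the same start year for treatment. SAP 4.2 says the national programme delivers the month-12 and month-24 rounds, but not that delivery differs by district. A 5-point gap would mean that district alone explains 6.25 of 18.75, a third of the residual variance, so it is an extreme case.

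Most of the precision gain in step 6 also comes from the covariate. At a 20-point imbalance without stratification, adjustment alone still gives about 1.57/√0.96 = 1.60 for the 5-point gap.

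All of these points stand. They limit the size of the concern, but they give no reason to prefer the present wording when restriction is available at this cost.

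**Conclusion.** The point holds as a cheap improvement to design and analysis. It is not evidence of an invalid trial. The stated 40 per arm is not guaranteed by the method described. District balance is left to chance, with a difference of 20 points or more between arms having probability about 5% to 12% over the assumed district splits and both readings of the method. District is also missing from the primary model. Simple randomisation of 80 communities with baseline adjustment remains a valid design.

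The benefit of changing depends on a district gap that the documents do not report: essentially none if there is no gap, a half-width of about 1.87 instead of 1.93 points at 2 points, and more if the gap is larger. The most concrete need is to state the scheme, because the permutation test in SAP 6.3 cannot be specified without it.

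**What to change.** 1. In Protocol 4.2.3 and SAP 3.2, replace the present wording with a one-step allocation of all 80 communities after the baseline visit, stratified by district, with equal numbers per arm within each district. Where the district counts are odd, the arms differ by at most one within a district, and the extra communities go to opposite arms so that the total is 40/40.
2. In SAP 6.2.1 (Aim 1), add district as a covariate in the primary model.
3. In SAP 6.3, state that the permutation test re-draws allocations under this same scheme.

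If allocation has already taken place, record which procedure was used and whether arm totals were fixed, add district as a prespecified covariate before unmasking, and re-draw permutations by the scheme actually used.

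The cost is a small change to the allocation code and one degree of freedom in the model. No communities, visits or samples are added.
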